Rate of AE of "residual Urine Volume"	Dichotomous 1=yes 0=no	The frequency of residual urine volume events will be taken from all adverse event reporting forms submitted for a participant. The outcome variable will be coded with a value of "Yes" if the participant had any reported residual urine events over their study duration, identified by MEDRA coding preferred term of "Residual urine volume". If no residual urine volume events were reported for a participant, the outcome variable will be coded with a value of "No".
		Final database lock review took efforts to query existing adverse events with terms such as "incomplete bladder emptying", "sensation of incomplete bladder emptying" for any post void residual assessments completed around the time of the event. Details from query responses helped with MEDRA coding the relevant level of severity ("Urinary Retention" vs. "Residual urine volume") accurately.
Complications after study intervention And Complication after cross- over study intervention	Dichotomous 1=yes 0=no	The frequency of complications after study intervention will be taken from Surgeon's Report forms submitted for a participant, for both the main study treatment and allowed Botox reinjection if applicable. The outcome variable for each specific complication will be coded with a value of "Yes" if ever reported over their study duration, otherwise it will be coded with a value of "No". If a participant experienced any complication after main study interventions, the composite indicator will be coded with a value of "Yes", otherwise coded to "No".
Bladder Injury Ureteral Injury		The frequency of complications after cross-over study intervention will be taken from any Off Protocol Surgeon's Report forms submitted for a participant The outcome

Variable	Туре	Definition	
Urethral Injury Vaginotomy		variable for each specific complication will be coded with a value of "Yes" if ever reported over their study duration, otherwise it will be coded with a value of "No". If a participant experienced any complication after a crossover study intervention, the composite indicator will be coded with a value of "Yes", otherwise coded to "No".	
		Note that all reported intervention complications are expected to have an accompanying adverse event form entered but may not be recorded as an adverse event to reduce database redundancy.	
Any catheter placement or intermittent self- catheterization 2 or more weeks post-procedure	Dichotomous 1=yes 0=no	The frequency of catheter placement or intermittent self-catheterization will be identified from self-catheterization (CISC) logs submitted for a participant. Additionally, adverse events that occurred 2 or more weeks after procedure reported with a "Catheter placement" action or have any text detailing self-catheterization in the comments field will also identify these cases. The outcome variable will be coded with a value of "Yes" if the participant has any reported CISC log or adverse events detailing self- catheterization, otherwise it will be coded with a value of "No".	
		Note that the Surgeon's Report form completed at time of study intervention contains questions regarding self-catheterization, but this outcome is specifically limited to timing greater than 2 weeks from study procedure.	
		Final database lock review took efforts to query sites for participants with reported self- catheterization logs or questionable post void residual results (>200mL, aside from visits immediately post-surgery) and get PI confirmation of self-catheterization in relevant adverse event comments.	
Any AE that is unexpected	Dichotomous	Participants will be coded to "Yes" if any adverse event was reported over their study	
and Related to intervention	1=yes	duration that had the following fields indicated on the form: Expected = "No"	
	0=no	Relationship = "Related"	
		Otherwise, the participant will be coded to "No".	

Variable	Туре	Definition	
Any Hospital admission or return to OR related to intervention	Dichotomous 1=yes 0=no	The frequency of hospital readmissions / returns to the operating room related to study intervention will be identified by searching for applicable terms and comments submin across all adverse events for a participant. If the participant has an event indicates hospital readmission or a return to the operating room and is reported as "Related", the indicator will be coded to "Yes", otherwise it will be coded to "No". At final database lock review, there were no adverse events reported as "related" that indicated a hospital readmission or return to the operating room.	
Pelvic Pain	Dichotomous 1=yes 0=no	The frequency of pelvic pain events will be taken from all adverse event reporting forms submitted for a participant. The outcome variable will be coded with a value of "Yes" if the participant had any reported pelvic pain over their study duration, identified by MEDRA coding preferred term of "Pelvic pain". If no pelvic pain events were reported for a participant, the outcome variable will be coded with a value of "No".	
Dyspareunia	Dichotomous 1=yes 0=no	The frequency of dyspareunia events will be taken from all adverse event reporting forms submitted for a participant. The outcome variable will be coded with a value of "Yes" if the participant had any reported dyspareunia over their study duration, identified by MEDRA coding preferred term of "Dyspareunia". If no dyspareunia events were reported for a participant, the outcome variable will be coded with a value of "No".	
Levator Syndrome	Dichotomous 1=yes 0=no	The frequency of levator spasm events will be taken from all adverse event reporting forms submitted for a participant. The outcome variable will be coded with a value of "Yes" if the participant had any reported levator spasms over their study duration, identified by MEDRA coding preferred term of "Levator syndrome". If no levator spasm events were reported for a participant, the outcome variable will be coded with a value of "No".	
Self-report New/worsening abdominal/genital pain (UDI item N)	Dichotomous 1=yes 0=no	Self-report of new or worsening abdominal/genital pain is captured in the UDI form item N at baseline and 6 months (and 3, 9, and 12 months). The outcome variable will be coded with a value of "Yes" if any post-baseline UDI assessment reported a worse bother than at baseline (ordered categories are "No", "Yes" with bother not specified / "Not at all", "Yes" and "Slightly", "Yes" and "Moderately, "Yes" and "Greatly"). For	

Variable	Туре	Definition	
		participants that did not have any post-baseline visits, the outcome variable will be set to missing. UDI item N: Do you experience pain in the lower abdominal or genital area?	
		Yes No (Skip to O.)	
		If yes, how much does it bother you?	
		□ Not at all □ Slightly □ Moderately □ Greatly	
Self-report New/worsening dyspareunia (PISQ item C5)			
		PISQ item C5: (completed only for sexually active)	
		How often do you feel pain during sexual intercourse? (If you don't have intercourse check this box \Box and skip to the next item.)	
		$1 \square$ Never	
		2 □ Rarely 3 □ Sometimes	
		4 □ Usually	
		5 🗆 Always	

Variable	Туре	Definition	
Self-report New/worsening difficulty emptying bladder (UDI item J)	Dichotomous 1=yes 0=no	Self-report of new or worsening difficulty emptying bladder is captured on the UDI for item J at baseline and 6 months (and 3, 9, and 12 months). The outcome variable will coded with a value of "Yes" if any post-baseline UDI assessment reported a worse bo than at baseline (ordered categories are "No", "Yes" with bother not specified / "Not all", "Yes" and "Slightly", "Yes" and "Moderately, "Yes" and "Greatly"). For participants that did not have any post-baseline visits, the outcome variable will be se missing.	
		UDI item J:	
		Do you experience difficulty emptying your bladder?	
		Yes No (Skip to K.)	
		If yes, how much does it bother you?	
Other AEs or symptoms of interest	Dichotomous 1=yes 0=no	 We will also look to see if there are any additional AEs to report on the AE table, covering the following: These will be identified via evaluation of AE preferred terms, verbatim descriptions/comments and AE relationship at least possibly related. Other MUS surgical wound healing problems >6 weeks New/worsening vaginal infection Other infection possibly related to intervention New/worsening partner dyspareunia 	
		At final database lock review, 2 additional event terms of interest were identified: "pyelonephritis", and "Gonococcal pelvic inflammatory disease". Appropriate indicator variables will be created for each additional term of interest, coded to "Yes" if the participant has any reported events coded to the respective MEDRA preferred term. The outcome variable will be set to "No", otherwise.	

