4.3 Study Arm Assignment and Randomization

The participant will be randomized to one of the two treatment arms (Botox A or MUS) using a web-based data management system. Randomization (1:1 to the two treatment arms) will be performed using permuted blocks, with a block size that is known only to the DCC and will be stratified by site and age group (≥ 65 , < 65). Once patients are enrolled and randomized, the intervention (either Botox A or mid-urethral sling) should be scheduled within 8 weeks from randomization. If treatment is not completed within 91 days of the baseline UDI, the baseline assessments are to be repeated.

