4.5 Masking and Data Lock

4.5.1 General Masking Procedures

It is not feasible to mask the patients or surgeons to the intervention due to the nature of the interventions. While a placebo for Botox A is possible through saline injection during midurethral sling surgery, sham sling surgery would require suprapubic and vaginal incisions that would expose patients to the risks of sedation/anesthesia for the Botox A group.

Outcome assessors will be masked to treatment assignment. All post-randomization outcome measures will be assessed by masked outcome assessors. All patient-reported outcomes (PROs) will be administered prior to other clinical assessments or procedures.

Study Individual	Masking
Study participant	No
Study surgeon	No
Outcome assessors	Yes

The senior statistician who reviewed and approved the SAP ([name]) also remained fully masked until database lock, and all study PIs were masked to cumulative results.

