4.5.2 Database Lock

Database lock and unmasking will occur when data collection has been completed and all data queries are resolved, and prior to the final data analysis. Prior to database lock a masked data review with the study PI (HH) will evaluate key data including study populations, protocol violations and completeness of key efficacy and safety data.

MUSA Study Visit	Screen/ Consent	Baseline/ Eligibility	Repeat Baseline*	Rando mizati on	Operation / Procedure	2 wk	3 mo	Botox- Reinj (Botox only)	Botox Reinj 2wk FU	6 mo	9 mo	12 mo	Close - out	Add' nl /As nec.
MUSA Data Collection Forms	Durat. 1-4 w	Duration 1-4 w	Prior Tx >91 d after UDI	w/in 8 wks pre Tx	Time 0	14 ± 7 d	91 ± 30 d		14 ± 7 d	183 ± 30 d	274 ± 30 d	365 ± 30 d		
Consent	Х													
§ UDI	Х		Х				Х			Х	Х	Х		
Bladder Diary		Х	Х				Х			Х		Х		
Demographics		Х												
Medical History / Medications		Х												
Eligibility		Х												
† Urodynamics		Х												
† POPQ		Х												
† PVR – Clinic Visit		Х				Х	Х	Х	Х	Х				
† Urine Dip		Х	Х		Х	Х	Х	Х	Х	Х				
Randomization				Х										
† Pregnancy Test					Х			Х						
† Surgeon report/ Complications					Х			Х						
Medical – follow up						Х	Х		Х	Х	Х	Х		

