4.6 Study Flow Chart of Assessments and Evaluations

MUSA Statistical Analysis Plan

· · · · · · · · · · · · · · · · · · ·		1						1	1		
§ OAB-q	Х	Х			Х		Х	Х	Х		
§ IIQ	Х	Х			Х		Х	Х	Х		
§ PISQ	Х	Х			Х		Х	Х	Х		
§ EQ-5D	Х	Х		Х	X	Х	Х	Х	Х		
§ SF-36/ SF- 6D	Х	Х		Х	Х	Х	Х	Х	Х		
§ PGI-S	Х	Х			X		Х	Х	Х		
§ Lost Productivity / Costs				Х	X	Х	X	X	X		
§ OAB-SAT-q					Х		Х	Х	Х		
§ PGI-I					Х		Х	Х	Х		
§ PGSC					Х		Х	Х	Х		
Final Status										Х	
Adverse Events											Х
Serious AE											Х
Protocol Viol. /Deviation											Х
CISC/PVR – Patient Reported											Х
Additional Therapies											Х
Additional Office Visits											Х

*Repeat baseline if not randomized and treatment not initiated within 90 days of the date UDI completed as part of the initial baseline visit.

[†] Performed in clinic only. MUS procedure urine dip collected per usual clinical practice.

§ Patient Reported Outcomes

Note; extended follow-up begins after the 6m visit.

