7.10 Assessment Windows

Baseline assessments were to be completed no longer than 3 months prior to intervention with assessments repeated if participant treatment is delayed for over 3 months. All other visits were completed at 2 weeks with $a \pm 1$ week window around the visit and 3-month intervals (3, 6, 9, 12 months) with $a \pm 1$ month window around the visit. Coordinators attempted to complete all follow-up visits, even if they couldn't be completed within window. For all analyses, all available data will be used regardless of if the assessment was completed within window or not.

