9.2 Variable Definitions

Primary and secondary efficacy variables as well as exploratory and safety outcomes are described in the table below.

Note that for any patient who had a repeat baseline, their repeat measures will be used in the definition of baseline (their updated baseline scores were entered into the repeat baseline CRF by the sites).

Variable	Туре	Definition
Primary Outcomes		
type of urinary incontinence	Categorical stress-predominant urgency-predominant balanced	 The definition of the type of urinary incontinence will be based on 2 questions of the Urogenital Distress Inventory, 1. "Do you experience urine leakage associated with a feeling of urgency?" 2. "Do you experience urine leakage related to physical activity, coughing, or sneezing?" Based on our inclusion criteria, patients must report at least "moderate" bother on both questions. If the subject reports greater bother on the stress question, she will be classified as stress-predominant MUI. If the subject reports greater bother on the urgency question, she will be classified as urgency-predominant MUI. If the subject reports equal bother on both questions, she will be classified as "balanced" MUI.
Change from baseline in UDI Total Score at 6 months (and at 3, 9, and 12 months) 6 months is primary,	Continuous	The Urogenital Distress Inventory-Total Score will be computed at baseline and 6 months (and 3, 9, and 12 months) using the standard scoring algorithm. Specifically, the instructions are to sum the Stress, Irritative, and Obstructive subscales of the UDI (see below). If any subscale scores are missing, then the score will be calculated as the sum of the non-missing scales. The outcome will then be computed as the difference in Total score at 6 months (and 3, 9, and 12 months) and the Total score at baseline. If data for an assessment time point are missing, the outcome variable will be coded as missing.

Variable	Туре	Definition
Secondary Outcomes		

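### A baseline UDI can be repeated after randomisation, when the woman knows her arm, and SAP 9.2 would then use it in the change score and as the covariate

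*SAP*

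**What the plan says.** **Which value counts as baseline.** SAP 9.2 says that "for any patient who had a repeat baseline, their repeat measures will be used in the definition of baseline". It does not ask whether the repeat came before or after randomisation. Baseline UDI total is subtracted to form the primary outcome (SAP 9.2) and is also a model covariate (SAP 7.2 and 9.3). No planned analysis uses the first value.

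**What triggers a repeat.** Four places speak to this:

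- SAP 4.3: "If treatment is not completed within 91 days of the baseline UDI, the baseline assessments are to be repeated". This directly follows the rule that the intervention "should be scheduled within 8 weeks from randomization".
- SAP 7.10: baseline is to be no more than 3 months before the intervention, "with assessments repeated if participant treatment is delayed for over 3 months".
- SAP flow chart, window for the repeat-baseline column: "Prior Tx >91 d after UDI".
- SAP flow chart, footnote: "Repeat baseline if not randomized and treatment not initiated within 90 days of the date UDI completed". The repeat column also stands to the left of the randomisation column.

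**Delay after randomisation.** Protocol 4.6 lets a randomised woman who is still untreated at 8 weeks stay in the study at the investigator's discretion. It gives no upper limit.

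**Masking.** SAP 4.5.1: "It is not feasible to mask the patients or surgeons to the intervention".

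**Already planned.** SAP 8.3 summarises by arm the time from baseline to treatment and the percentage above 91 days. The protocol text supplied has no repeat-baseline rule, and SAP 13 does not list one as a change.

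**The concern.** A baseline should be fixed before assignment. Two of the four triggers (SAP 4.3 and 7.10) and the flow-chart window count to treatment, which always follows randomisation. A woman whose treatment slips could therefore complete a second UDI knowing whether she will have an injection or a sling, and SAP 9.2 would make that her baseline.

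The UDI is self-reported. Protocol 3.4.1.a itself rejects a single global-impression item as primary outcome because unmasked women's answers could be biased. The UDI has many items, but its source is the same.

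If assignment shifts the repeated score differently in the two arms, or if repeats are more common in one arm, mean recorded baseline differs between arms for a reason other than chance. That difference enters the change score in full and the adjusted estimate in part.

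**Working it through.** **1. The plan's own figures reproduce.** With a difference of 26, SD 46.5, two-sided alpha 0.05 and power 90%, the two-sample t calculation gives 68.2, rounded up to 69 per arm. 69/0.95 = 72.6, so 73 per arm and 146 in total. Power at 23 points with 69 per arm is 82.2%, against the stated 82%. None of these figures is in dispute, and the fix changes none of them.

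**2. Can a repeat fall due after randomisation?** The windows are screening up to 4 weeks, baseline up to 4 weeks, and randomisation to treatment up to 8 weeks.

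- UDI at screening (SAP flow chart; protocol 4.4 also has it given on entry to confirm bother): 28 + 28 + 56 = 112 days, above 91. With the shortest screening and baseline windows: 7 + 7 + 56 = 70 days.
- UDI at baseline (protocol Table 9): 28 + 56 = 84 days, below 91. A repeat then needs a delay past the windows, which protocol 4.6 allows.

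So a post-randomisation repeat is possible on either schedule. On the second it cannot occur with every window met.

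**3. Size in the adjusted analysis.** Let f be the share of each arm with a post-randomisation repeat, and d the shift of one arm's repeat values relative to the other's. Mean recorded baseline then differs between arms by f × d. The covariate absorbs part of this; what remains is b × f × d, where b is the slope of follow-up on baseline.

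Protocol Table 6 (ESTEEM, UDI total) gives SD 43 at baseline, 55 for change and 46 for change from the model. Crediting the whole reduction to baseline:

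b = 1 − √(55² − 46²)/43 = 1 − 30.15/43 = 0.30.

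With 46.5 in place of 46, b = 1 − 29.37/43 = 0.32. The ESTEEM model also adjusted for site, so some of the reduction may not belong to baseline; b would then be larger.

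Standard error with 69 per arm: 46.5 × √(2/69) = 7.9.

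The values of f and d below are assumptions, because the documents give neither. Power is the normal approximation at a true difference of 26 with the bias running against it; without bias it is 90.7%.

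| f | d (points) | Raw change, f × d | Adjusted, b × f × d | Power |
|---|---|---|---|---|
| 5% | 5 | 0.25 | 0.07 | 90.6% |
| 10% | 10 | 1.0 | 0.30 | 90.1% |
| 20% | 13 | 2.6 | 0.78 | 89.0% |
| 20% | 26 | 5.2 | 1.55 | 87.0% |
| 30% | 26 | 7.8 | 2.33 | 84.8% |

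The largest case is 2.33/7.9 = 0.29 standard errors, or 2.33/26 = 9% of the MID. For 20% and 26 points, b = 0.5 would give 0.5 × 5.2 = 2.6 points and 84% power.

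A simulation of 6,000 trials at b = 0.30 gave a bias of 1.6 points and a type I error of 0.055 for 20% and 26 points, and 2.2 points and 0.058 for 30% and 26 points. Its control run without repeats returned 0.24 where 0 is expected, so the simulated biases are good to a few tenths of a point.

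**4. Uses without covariate protection.** SAP 9.5.3 compares between arms the percentage of women whose unadjusted change reaches the MID. SAP 7.9 classifies women as stress-predominant, urgency-predominant or balanced from baseline UDI items, so a repeat could reclassify a woman after assignment. Both are supportive. The effect on the percentages cannot be computed from the documents.

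**The case against.** **The footnote.** Read literally, it confines repeats to women not yet randomised, and the column order agrees. If that was the practice, no post-randomisation baseline exists. This is the strongest counter-argument, and it means the plan cannot be said to repeat baselines after randomisation, only to allow it. It does not settle the matter. On that reading the treatment condition is redundant, since an unrandomised woman has had no study treatment. The footnote also conflicts with SAP 4.3, SAP 7.10 and its own column's window, and it counts 90 days rather than 91.

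**Timing.** A reader might infer from the 112-day sum that such repeats arise routinely within the windows. The sum needs all windows at their maximum and the UDI at the start of screening, and protocol 4.4 aims for surgery within 2 months of enrolment.

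**Rationale.** Time 0 is the procedure and the outcome is change after treatment. A repeat is still pre-treatment and avoids measuring change from a score more than 3 months old. This has merit, and a sensitivity analysis preserves it.

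**Existing reporting.** The by-arm summary above 91 days in SAP 8.3 would show unequal delay. It would not show how many repeats followed randomisation.

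**Delay by arm.** A reader might infer that an office procedure and an operating-room procedure must be delayed unequally. Both share the 8-week target. Protocol 5.2.2 reschedules Botox after a positive urine dip, whereas the sling dip follows usual practice (SAP flow chart), and SAP 9.2 notes 8 UTIs between randomisation and treatment. Their arm is not stated, so unequal delay is possible but not shown.

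**Conclusion.** The point stands as a minor one. Under SAP 4.3, 7.10 and 9.2 with protocol 4.6, an unmasked post-randomisation UDI can become the baseline of the primary endpoint, and the flow-chart footnote that might prevent this contradicts the other passages.

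The bias in the adjusted 6-month difference is about 0.1-2.3 points. This rests on assumed repeat shares of 5-30%, assumed between-arm shifts of 5-26 points, and a slope of about 0.30 taken from ESTEEM. It is small beside the 26-point MID and the standard error of about 7.9.

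Two stronger conclusions are not supported. The first is that the primary result is materially biased: the number of post-randomisation repeats is not given, and adjustment removes most of any shift. The second is that the MID estimates themselves carry the full unadjusted shift: SAP 9.5.3 derives them from contrasts between anchor categories and from the baseline SD, not from a contrast between arms. Only the responder percentages compare arms on unadjusted change.

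**What to change.** In SAP 9.2, define baseline for the primary analysis and for the UDI-type subgroup as the last UDI completed before randomisation. Use a repeat only if it precedes randomisation. The secondary UDI outcomes follow the primary model (SAP 9.4) and should take the same definition.

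Run the primary model once more with the repeat-based baseline as a sensitivity analysis.

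Add the number of post-randomisation repeats by arm to the summary already planned in SAP 8.3, and state there that time to treatment counts from the first UDI.

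Reconcile SAP 4.3, SAP 7.10, the flow-chart window and its footnote on who repeats and on 90 versus 91 days. If the footnote reflects what was done, say so in SAP 9.2, and the question closes.

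Cost: a few lines of SAP text and one extra model run. The sample size is unchanged. The downside is an older baseline for women with a long wait, which adds slight noise.
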